7 SAFETY ASSESSMENTS

7.1 Specification of Safety Parameters

All patients will be closely monitored both intra and post operatively for bleeding that is in excess of normal cesarean delivery estimated blood loss (EBL). If vital signs are deranged in any fashion this will prompt laboratory and clinical assessment that meets standard of care irrespective of study participation (for example, HR >120, SBP <90>160, DBP <50>90, temp >38.0 C, RR >22<8).

Hemoglobin values that are < or equal to 7.0 g/dL will warrant transfusion; also, if patients have hemoglobin values that are above this threshold but active ongoing bleeding is suspected clinically, then preparations may also be made for transfusion. In no way will standard of care post operatively at RMH be compromised based on study inclusion.

7.2 Methods and Timing for Assessing, Recording, and Analyzing Safety Parameters

To our knowledge, there has not been a randomized controlled trial investigating the safety of salpingectomy compared to tubal ligation at the time of cesarean delivery in women desiring permanent sterilization. A study performed retrospectively in 2014 of over 40,000 women in Canada showed that when performed at the time of hysterectomy, salpingectomies did not increase operative risks and was feasible(5). The concern with performing a salpingectomy post-delivery is that the uterus and its blood vessels are quite enlarged. A salpingectomy removes more of the tissue along the mesosalpinx which can be associated with quite large vessels. This theoretically may increase the risk of disrupting these large vessels which may lead to excessive blood loss, need for blood and further surgery that may lead to the loss of the adnexa and or uterus. However, the sterilization will only take place if the patient is clinically stable for the procedure.

Danis et al recently published data on a cohort of 16 patients undergoing a salpingectomy after a vaginal delivery through an umbilical incision matched with 64 controls undergoing a BTL through a similar incision.(6) No increased risk of bleeding or complications was noted in the study group. This suggests that salpingectomy as a method of sterilization in a recently pregnancy-enlarged uterus may be equivocal in safety to the standard BTL.

After each set of 20 patients are enrolled, the study team will evaluate the operative reports of enrolled patients for evidence of adverse events.

7.3 Adverse Events and Serious Adverse Events

Adverse Event: Is defined as any unfavorable and unintended sign (including an abnormal laboratory finding), symptom or disease temporarily associated with the use of a medical treatment or procedure that may or may not be considered related to the

medical treatment or procedure.

Adverse events are classified according to their severity.

Grade 1: Mild; asymptomatic or mild symptoms; clinical or diagnostic observations only; intervention not indicated.

- Increased pain score
- Mild anemia

Grade 2: Moderate; minimal, local or noninvasive intervention indicated

- Severe anemia not requiring transfusion

Grade 3: Severe or medically significant but not immediately life-threatening hospitalization or prolongation of hospitalization indicated; disabling limiting self-care.

- Severe anemia requiring transfusion
- Loss of one or both adnexa

Grade 4: Life threatening consequences; urgent intervention needed

- Requiring Cesarean hysterectomy
- Return to operating room

Grade 5: Death related to AE

Adverse outcomes are also problems/events that in the opinion of the principal investigator may have adversely affected the rights, safety, or welfare of the subjects or others, or substantially compromised the research data.

Given that a cesarean delivery will have also been performed prior to the tubal surgery, it will be difficult to distinguish if adverse events or serious adverse events are the direct result of the cesarean or the salpingectomies. Detailed review of the operative note will provide clarification as to which portion of the procedure is thought to have contributed to any adverse events.

7.4 Reporting Procedures

Patients enrolled in the trial will be monitored post-operatively according to standard of care in the hospital inpatient unit. Once the patient is discharged from the hospital, a routine postpartum visit will be ordered at 6 weeks. In the interim, any study patient returning to the hospital will be reported to the principal investigator and prompt a chart review.

The specimens from the sterilization procedures will be sent to pathology and undergo evaluation per protocol. Results will be reported back to the surgeon performing the procedure when completed.

7.5 Follow-up for Adverse Events

Adverse events will be followed immediately per standard of care for all surgical patients while in the immediate inpatient postoperative period and also if outpatient follow up is required. If a patient presents to an outside hospital for evaluation of a complication that is thought to be due to the procedure performed in the study, this will be captured in the 6 week post procedure follow up by speaking directly with the patient or the patient's representative and requesting a copy of the care provided at the outside hospital.

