Prior to the procedure a preoperative CBC will be performed. Patients will undergo the cesarean delivery and once stable from that procedure, will progress to either salpingectomy or bilateral tubal ligation per the randomization. Time from start to conclusion of the sterilization procedure will be logged to obtain operative time. Post procedure, the type of sterilization procedure will be disclosed to the patient. A postoperative CBC will be performed the next day at least 24 hours but no later than 48 hours after the conclusion of the procedure. In addition to standard patient demographics (age, race, parity, body mass index, etc), data collection will include procedural complications, return to the OR, length of stay, and postoperative complications including readmission within 6 weeks.

The primary outcome is mean drop in hemoglobin. Previous studies have reported a mean (SD) drop in hemoglobin of 1.32 (0.94) g/dl following a repeat cesarean delivery

and 1.40 (1.2) following a first cesarean delivery (7). Based on our experience in 2015, we anticipate that over 75% of our cases will be repeat cesarean deliveries. Assuming that a difference of 0.5 in the drop in hemoglobin between study arms would be considered as equivalent and assuming a common standard deviation of 1.1, the study will have 80% power to test for non-inferiority with 60 patients in each arm (120 totals). This calculation is based on a two-group 0.05 1-sided t-test of equivalent in means.

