7.7 Reporting Procedures

At each contact with the subject, the study team must seek information on adverse events by specific questioning and, as appropriate, by examination. Information on all adverse events should be recorded immediately in the source document, and also in the appropriate adverse event section of the case report form (CRF). All clearly related signs, symptoms, and abnormal diagnostic, laboratory or procedure results should be recorded in the source document.

All adverse events occurring during the study period must be recorded. The clinical course of each event should be followed until resolution, stabilization, or until it has been ultimately determined that the study treatment or participation is not the probable cause. Serious adverse events that are still ongoing at the end of the study period must be followed up, to determine the final outcome. Any serious adverse event that occurs after the study period and is considered to be at least possibly related to the study treatment or study participation should be recorded and reported immediately.

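### Section 7.5 ties the capture of outside-hospital complications, and the request for their records, to perceived causation, which is inconsistent with Sections 6.2.2, 7.3, 7.4 and 7.7

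*Combined protocol and SAP*

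**What the plan says.** Section 7.5 deals with women who seek care elsewhere. Its rule concerns "a complication that is thought to be due to the procedure performed in the study, this will be captured" at the six-week follow-up. The method is "by speaking directly with the patient or the patient's representative and requesting a copy of the care provided at the outside hospital". It gives no rule for outside presentations not attributed to the procedure, and does not say who makes the attribution.

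The other safety provisions carry no causal condition:

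- Section 7.4: "any study patient returning to the hospital will be reported to the principal investigator and prompt a chart review".
- Section 7.7: "All adverse events occurring during the study period must be recorded", with specific questioning at each contact.
- Section 7.3: an adverse event is one linked in time to a medical treatment or "procedure that may or may not be considered related to the" treatment or procedure.
- Section 6.2.2: untoward events after the first 24 hours are reviewed up to the postpartum visit, and the coordinator telephones women whose postpartum care is elsewhere.

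On attribution, 7.3 concedes that "it will be difficult to distinguish if adverse events or serious adverse events are the direct result of the cesarean or the salpingectomies", and then relies on the operative note: "Detailed review of the operative note will provide clarification as to which portion of the procedure is thought to have contributed".

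On knowledge of the arm, 6.2.2 has the allocation given to the surgical team before surgery. Section 3 says: "Post procedure, the type of sterilization procedure will be disclosed to the patient".

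**The concern.** The same complication is handled differently according to where the woman seeks care. If she returns to the study hospital, her chart is reviewed whatever the cause. If she goes elsewhere, the step in 7.5 depends on someone first judging that the procedure caused the problem. That judgement comes after the participant and the surgical team know the arm, and the protocol itself calls it difficult.

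Complications and readmission are secondary outcomes compared between arms (Sections 1.2, 3, 9.4.2 and 9.5), and the trial is presented as one of safety. Randomization balances the cesarean background, so comparing all events needs no causal judgement. If a judgement made with the arm known decides which outside events are documented, or captured at all, the comparison is no longer protected by randomization. The distortion could run either way: against salpingectomy if the newer procedure is blamed more readily, or toward apparent safety if its complications are put down to the cesarean.

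**Working it through.** **1. The provisions side by side**

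| Section | What it covers | Causal condition? | Outside records requested? |
|---|---|---|---|
| 6.2.2 | Untoward events from after 24 hours to the postpartum visit; telephone call if care is elsewhere | No | Not mentioned |
| 7.3 | Definition of an adverse event | No | Not applicable |
| 7.4 | Any return to the hospital | No | Not mentioned; chart review |
| 7.5 | Outside-hospital complication | Yes | Yes |
| 7.7 | All adverse events, asked about at each contact | No | Not mentioned |
| 9.4.2 | Complications in the operative report and medical record | No | Not mentioned |

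Two things follow. First, 7.5 alone has a causal condition, and nothing says whether it or the general rule in 7.7 takes precedence. Second, 7.5 alone provides for outside records. Section 9.4.2 takes complications from the operative report and medical record, and 10.2 has data abstracted from the electronic record and case report forms. An attributed outside event would therefore have source documents. An unattributed one, even if recorded under 7.7, may rest on what the woman remembers, and so may its 7.3 grade.

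Section 8 points the same way: events are counted by grade first, and a committee considers causation only after a hold.

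**2. The plan's own figure**

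The plan gives no figure for this point. Its only design figure is the sample size, used here just as a denominator. With margin 0.5, SD 1.1, one-sided alpha 0.05 and 80% power, n per arm = 2 × (1.645 + 0.842)² × 1.1² / 0.5² = 59.9, so 60. This agrees with Section 9.2.

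**3. Illustration of size (all inputs assumed)**

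The documents give no complication rate, no share of events seen elsewhere and no capture probability. Let p be the true risk, equal in both arms; s the share of events seen outside; and c the fraction of outside events captured. Observed risk = p × (1 − s + s × c), and the false difference between arms = p × s × (difference in c). With c of 0.9 in one arm and 0.5 in the other:

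- p = 5%, s = 10%: 4.95% vs 4.75%; difference 0.2 points, or 0.12 events per 60.
- p = 10%, s = 25%: 9.75% vs 8.75%; difference 1.0 point, or 0.6 events per 60.
- p = 15%, s = 50%: 14.25% vs 11.25%; difference 3.0 points, or 1.8 events per 60.

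Swapping the two values of c reverses the sign. If 7.7 is followed fully, c = 1 in both arms and the false difference in counts is 0. If c is instead read as the fraction of outside events backed by records, the same products give the gap in source-documented events, which can arise even when 7.7 is followed.

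As apparent risk ratios among post-discharge events, with true risk equal, 7.5 used as a filter, and outside shares of 20% and 40%:

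- Attribution 70% vs 30%: 0.94/0.86 = 1.09 and 0.88/0.72 = 1.22.
- Attribution 60% vs 40%: 0.92/0.88 = 1.05 and 0.84/0.76 = 1.11.
- Attribution 50% in both arms: ratio 1, with 10% to 20% of events missed in each arm.

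Complications already in the operative report would dilute these ratios.

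**The case against.** A reader might infer that the plan captures outside complications only when they are attributed, and so will lose events unequally by arm. The documents do not support that. The word only does not appear in 7.5. Section 7.7 requires every adverse event to be recorded and asked about at each contact, the schedule in 6.1 lists adverse events at six weeks, and 6.2.2 adds the all-cause review and the telephone call. Section 7.5 can fairly be read as an extra step for obtaining records, not a limit on recording. This stands, and it rules out any claim that loss is built into the plan.

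Three further objections carry weight:

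- The procedure in 7.5 may include the cesarean, since 7.3 speaks of portions of the procedure. If so, an event blamed on the cesarean still meets the condition, and much of the route to unequal handling closes. The text does not settle which reading applies.
- Section 7.3 names only salpingectomy beside the cesarean. A reader might infer that BTL events will be dropped. But that sentence is about attribution, not capture, and the next one is neutral between arms.
- Section 7.5 does not say who judges, so it is not established that this person knows the arm. What can be said is that the participant and surgical team know it and no blinded assessor is described.

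None of this answers the point about records: 7.5 remains the only route to them, and it is conditional. The operative note is limited help, because it names the procedure and predates any post-discharge complication.

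**Conclusion.** The point holds as an inconsistency between sections. Followed literally, 7.5 can give selective source documentation and grading of outside-hospital events, and possibly selective capture, on a judgement with no blinding described. Loss of events is possible but not shown.

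The size cannot be derived from the documents. The range of 0.2 to 3.0 percentage points and the risk ratios of 1.05 to 1.22 rest wholly on assumed rates, outside shares and capture or attribution fractions. They show scale and are not predictions; the direction is unknown. A gap of up to about 1.8 events per 60 is modest in absolute terms, but matters where harms are few.

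Only the secondary complication and readmission outcomes are exposed. The primary outcome, measured at 24 to 48 hours, is unaffected. This is a cheap improvement, not a threat to the trial's main conclusion.

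**What to change.** In 7.5, delete the clause after the word complication that makes the provision depend on the study procedure being thought the cause. Every outside-hospital presentation through six weeks is then captured, and its records requested, in both arms and whatever the perceived cause. This brings 7.5 into line with 7.7.

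In 9.4.2 or 9.5, state that complications and readmissions are compared between arms on all events, with attribution reported descriptively. Relatedness should be judged as a separate step, preferably by someone unaware of the arm.

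Optionally, name both sterilization procedures in the 7.3 sentence on attribution. This is clarification only.

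The cost is a small amount of protocol wording and a few more record requests at a follow-up already planned. Some unrelated events will enter the counts and add a little noise. The change is worthwhile on either reading of 7.5: it removes a possible source of bias, or makes explicit what 7.7 already requires.

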7.6 Safety Monitoring

A data safety monitoring plan (DSMP) will be filed as an attachment to the protocol. The primary elements of which include the following:

- Review of charts after the first 10 patients and then at least quarterly thereafter.
- Placement of study on hold if a trend in adverse events are noted.

7.7 Reporting Procedures

At each contact with the subject, the study team must seek information on adverse events by specific questioning and, as appropriate, by examination. Information on all adverse events should be recorded immediately in the source document, and also in the appropriate adverse event section of the case report form (CRF). All clearly related signs, symptoms, and abnormal diagnostic, laboratory or procedure results should be recorded in the source document.

All adverse events occurring during the study period must be recorded. The clinical course of each event should be followed until resolution, stabilization, or until it has been ultimately determined that the study treatment or participation is not the probable cause. Serious adverse events that are still ongoing at the end of the study period must be followed up, to determine the final outcome. Any serious adverse event that occurs after the study period and is considered to be at least possibly related to the study treatment or study participation should be recorded and reported immediately.

7.8 Follow-up for Adverse Events

All unresolved adverse events should be followed by the principal investigator until the events are resolved, the subject is lost to follow-up, or the adverse event is otherwise explained. At the last scheduled visit, the coordinator or principal investigator should instruct each subject to report, any subsequent event(s) that the subject, or the subject's personal physician, believes might reasonably be related to participation in this study.

8 INTERVENTION DISCONTINUATION

Criteria for Discontinuation of Study or Early Stopping include:

1. More than 20 cases Grade 1 or 2 adverse events
2. More than 3 cases of Grade 3 adverse events
3. Any case of Grade 4 or Grade 5 adverse events

If the above criteria for discontinuation are met, the study will be put on clinical hold. A Data Monitoring and Safety committee will be convened to assess the causal linkage between the adverse events and the procedure. If causal linkage is established, the study will be permanently stopped. If no causal linkage is established the study will be taken off hold. Participants will continue to be followed, with their permission, even if the study is discontinued.

The study may be discontinued at any time by the IRB, the OHRP, the FDA, or other government agencies as part of their duties to ensure that research participants are protected.

Safety data on any subject discontinued due to an AE or SAE will be collected. Subjects will be given appropriate care under medical supervision until the symptoms of any AE resolve or the subject's condition becomes stable.

Subjects may withdraw voluntarily from participation in the study at any time and for any reason.

9 STATISTICAL CONSIDERATIONS

9.1 General Design Issues

The null hypothesis in this non-inferiority trial is that the mean difference in pre and postoperative hemoglobin of patients undergoing salpingectomy will be lower than that for patients undergoing BTL at the time of cesarean delivery by at least 0.5 g/dl. The alternative hypothesis to be proven is that this difference will be no lower than 0.5 g/dl.

A non-inferiority trial was chosen as the study aims to compare a less commonly performed procedure with a known and accepted standard. We want to show that the less common procedure is at as safe as the standard. Patients will be randomly assigned to salpingectomy or BTL at enrollment.

Primary hypothesis: The alternative hypothesis to be tested is that the mean difference in pre and postoperative hemoglobin of patients undergoing salpingectomy will be no lower than those that undergoing BTL at the time of cesarean delivery.

Primary variable: Mean hemoglobin change

9.2 Sample Size and Randomization

The primary outcome is mean drop in hemoglobin. Previous studies have reported a

mean (SD) drop in hemoglobin of 1.32 (0.94) g/dl following a repeat cesarean delivery and 1.40 (1.2) following a first cesarean delivery (7). Based on our experience in 2015, we anticipate that over 75% of our cases will be repeat cesarean deliveries. Assuming that a difference of 0.5 in the drop in hemoglobin between study arms would be considered as equivalent and assuming a common standard deviation of 1.1, the study will have 80% power to test for non-inferiority with 60 patients in each arm (120 total). This calculation is based on a two-group 0.05 1-sided t-test of equivalent in means.

9.2.1 Treatment Assignment Procedures

Once enrolled and consented, women will be randomized using a stratified block randomization algorithm prepared by the study statistician to either standard BTL or salpingectomy stratified according to number of prior cesarean deliveries (first versus repeat), and BMI (BMI < 35, BMI > 35).

9.3 Interim analyses and Stopping Rules

No interim analysis is planned.

The study will be stopped or placed on clinical hold if the number of adverse events exceeds the thresholds detailed in section 8.

9.4 Outcomes

9.4.1 Primary outcome

The primary outcome is mean change in preoperative to postoperative hemoglobin. These values will be collected from the patient's chart. The preoperative hemoglobin will be performed on the day of surgery. The postoperative hemoglobin will be performed the morning after surgery at least 24 hours but no greater than 48 hours after the procedure.

9.4.2 Secondary outcomes

1. Time in minutes in performance of BTL vs salpingectomy: Start time and stop time will be articulated by the surgeon and recorded by the circulating RN or other obstetrical provider on a case report form. Total time will be calculated
2. EBL in ml as documented in the operative report.
3. Complications as documented in the operative report and medical record
4. Pain scores as documented in patient chart

9.5 Data Analyses

A 1-sided 95% confidence interval will be constructed for the difference between study arms in the mean drop in hemoglobin. In addition, the reduction in hemoglobin will be analyzed using a one-sided T-test using a change of .5g/dL. Secondary endpoints will be analyzed using two-sided T-test testing for a difference between the two study arms or a Chi-square test as appropriate. Statistical significance will be determined using a p-value of 0.05.

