6.2.2 Enrollment, Baseline, and/or Randomization

Enrollment

Patients will be considered for enrollment if they meet inclusion criteria (please refer to section 4.1). If a patient expresses a desire to undergo permanent sterilization to her provider at any time and will undergo a cesarean delivery then she is eligible for enrollment and the study coordinator will be contacted to introduce the study and obtain informed consent.

In the event the study coordinator is not available for consent (i.e., middle of the night, spontaneous onset of labor in a patient planning repeat cesarean for delivery), then an obstetrical provider listed in the IRB will be able to obtain consent for enrollment. The delivering provider will not obtain consent.

Randomization

- Initiation of study intervention relative to randomization: When patients have been enrolled in the study they will be randomized. The Dynamic Allocation System will be used for electronic randomization based on the stratification criteria. Outcome of randomization (arm) will be communicated to the surgical team prior to surgery and to the participant following surgery.
- After cesarean delivery has been performed and the surgeon feels it is safe to proceed with surgical sterilization procedure identified from randomization (salpingectomy vs BTL), the start and stop time of the surgical procedure will be recorded by the circulating RN or other obstetrical provider on a case report form. Total time of the procedure, in minutes, will be recorded.

Follow-up Visits (abstracted from the Electronic Medical Record)

- Visit 1 (24 hours post operatively)
 - Vital signs
 - Physical exam
 - Medications
 - Hemoglobin
 - Adverse events
- Visit 2: Scheduled post-partum exam 6 weeks post procedure.
 - Vital signs
 - Physical exam
 - Medications
 - Adverse events

Completion/Final Evaluation

Final visit will be at the patient's postpartum exam. Any untoward events from after the first 24 hours from the procedure to that time will be reviewed (i.e., blood transfusion, readmission to hospital, etc.). If the participant receives post-partum care at a local clinic, not Mayo Clinic Rochester, the study coordinator will call the participant to collect final evaluation data, using an IRB-approved telephone script.

Patients who decide to withdraw from the study will also be interviewed and reasons for this will be discussed and potential reasons explored.

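### The tests in 9.5 leave out the two stratification factors: the planned test stays valid, but any precision gained by stratifying goes unused

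*Combined protocol and SAP*

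**What the plan says.** Allocation depends on two binary factors. Section 9.2.1 states that "women will be randomized using a stratified block randomization algorithm prepared by the study statistician", with arms "stratified according to number of prior cesarean deliveries (first versus repeat), and BMI (BMI < 35, BMI > 35"). Section 3 says the same. Section 6.2.2 names a different mechanism but the same criteria: "The Dynamic Allocation System will be used for electronic randomization based on the stratification criteria".

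The analysis in 9.5 does not return to these factors. For the primary outcome, "A 1-sided 95% confidence interval will be constructed for the difference between study arms in the mean drop in hemoglobin", and "the reduction in hemoglobin will be analyzed using a one-sided T-test using a change of .5g/dL". For the rest, "Secondary endpoints will be analyzed using two-sided T-test testing for a difference between the two study arms or a Chi-square test as appropriate". No model, covariate or stratum is named there or elsewhere. The sample size in 9.2 rests on the same two-group comparison: "This calculation is based on a two-group 0.05 1-sided t-test of equivalent in means".

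The two parts of the primary analysis differ in what they leave out. The t-test is unadjusted by definition. For the confidence interval the plan is silent on method.

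**The concern.** Balancing the arms on a factor that predicts the outcome removes that factor's variation from the difference between arms. An ordinary two-group t-test still counts that variation in its standard error. The computed standard error is then larger than the true one, and the interval is wider than the design requires. An analysis that includes the stratification factors brings the two back into line.

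The stake is efficiency. The plan has little power to spare: 60 per arm gives almost exactly 80%. There is also a smaller prespecification issue. Because the interval method is not named, both an adjusted and an unadjusted bound remain open once the data are seen, and near the 0.5 g/dL margin they could fall on different sides.

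**Working it through.** **Inputs from the plan (9.2).** Margin 0.5 g/dL; common SD 1.1; one-sided alpha 0.05; 60 per arm; mean (SD) drop 1.32 (0.94) after repeat and 1.40 (1.2) after first cesarean; over 75% repeat.

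**Step 1: the plan's sample size.** n per arm = 2 × [1.1 × (1.6449 + 0.8416) / 0.5]² = 59.85, rounded up to 60. The stated figure reproduces. The standard error of the arm difference is 1.1 × √(2/60) = 0.2008. With the exact t distribution (118 df, critical value 1.658, noncentrality 0.5/0.2008 = 2.490), power is 79.7%. The normal approximation gives 80.1%.

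**Step 2: the cesarean factor.** At 75% repeat:
- between-stratum variance = 0.75 × 0.25 × (1.40 − 1.32)² = 0.0012
- within-stratum variance = 0.25 × 1.2² + 0.75 × 0.94² = 1.0227
- R² = 0.0012 / 1.0239 = 0.0012, about 0.1%

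Setting the 0.0012 against the planning variance of 1.21 instead gives 0.0010. The standard error moves from 0.2008 to 0.2007, true one-sided error is 4.99%, and power is 79.7% with or without adjustment. A repeat share above 75% makes R² smaller still.

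**Step 3: both factors together.** The documents give no BMI effect, so total R² is an assumption and is shown as a range. With the arms balanced within strata:
- true standard error = 0.2008 × √(1 − R²)
- error of the unadjusted test = P(T₁₁₈ > 1.658 / √(1 − R²))
- unadjusted power: noncentral t, 118 df, noncentrality 2.490 / √(1 − R²), threshold 1.658 / √(1 − R²)
- adjusted power: same noncentrality, 116 df, threshold 1.658

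| Assumed R² | True SE | Error, unadjusted | Power, unadjusted | Power, adjusted |
|---|---|---|---|---|
| 1% | 0.1998 | 4.9% | 79.8% | 80.0% |
| 5% | 0.1957 | 4.6% | 80.3% | 81.4% |
| 10% | 0.1905 | 4.2% | 80.9% | 83.3% |
| 20% | 0.1796 | 3.3% | 82.3% | 86.9% |

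**Step 4: what those R² values require.** The cesarean factor supplies almost nothing, so BMI group must supply nearly all of R². With an even BMI split, which is the most favourable case, R² = 0.25 × d² / 1.21, where d is the difference in mean drop between BMI groups. Values of 1%, 5%, 10% and 20% need d of about 0.22, 0.49, 0.70 and 0.98 g/dL. An uneven split needs more. For scale, the margin is 0.5 and the expected mean drop is 0.75 × 1.32 + 0.25 × 1.40 = 1.34.

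**Step 5: simulation check.** Four strata, blocks of 4 and 35% in the higher BMI group (the last two are assumptions), the plan's stratum SDs, 15,000 runs per setting. With BMI explaining 5% and 10%, unadjusted error was 4.6% and 4.1%, and adjusted error 5.1% and 4.9%. With no BMI effect the two were 5.3% and 5.4%. The simulation standard error is √(0.05 × 0.95 / 15,000) = 0.18 points, so these lie within about two standard errors of 5%.

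**The case against.** The strongest reply is that nothing is broken. The only stratum difference in the documents is 0.08 g/dL, and at that size adjustment changes nothing. Every visible gain rests on a BMI effect that the plan neither states nor supports, and an R² of 5% already needs a BMI-group difference about as large as the whole margin. All of this stands, and it sets the size of the point.

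Three stronger readings are tempting, and the documents do not support them.

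- A reader might infer that the 5% error rate is compromised. The departure can only be toward conservatism. True error is at or below 5%, so the omission does not raise the chance of wrongly declaring non-inferiority.
- A reader might infer that planned power is lost. In the table, unadjusted power is never below the 79.7% of the stated design and rises slightly with R². What is forgone is an additional gain.
- A reader might infer a larger loss for operative time and estimated blood loss. The plan gives no variance, stratum effect or reason for choosing the strata that would support this. The general argument does apply to those outcomes: a standard error that is too wide makes a difference harder to detect. Its size there is unknown.

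The reply does not remove the mismatch itself. Adjustment costs almost nothing if the strata turn out not to be prognostic, and the interval method still needs naming. Nor does the point depend on whether stratified blocks or the Dynamic Allocation System is used, provided the system balances on these factors.

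**Conclusion.** The point holds as a conditional efficiency gain of low severity. The design stratifies on two factors and the named tests ignore both. The planned t-test is valid, and the 60 per arm stands. The documented cesarean effect gives no measurable gain. With an assumed total R² of 5% to 20%, adjustment would add about 1 to 5 points of power (81.4 − 80.3 = 1.1; 86.9 − 82.3 = 4.6), and the unadjusted test would run at 4.6% down to 3.3% instead of 5%. Those figures assume SD 1.1, no true difference between arms for power, near-exact balance within strata, and a BMI effect for which the documents give no evidence either way.

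**What to change.** In 9.5, state that the arm difference in hemoglobin drop will be estimated from a linear model with arm, first/repeat cesarean and BMI group. Non-inferiority is judged by comparing that model's one-sided 95% bound with 0.5 g/dL. Use the same terms for the continuous secondary outcomes, and keep the plain two-group t-test as a supportive analysis.

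So that the model terms are unambiguous, settle three details of the strata in the same edit:
- BMI of exactly 35 belongs to neither group in Section 3 or 9.2.1.
- The Précis names both factors in one place and only cesarean order in another.
- Sections 9.2.1 and 6.2.2 name different allocation mechanisms.

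The cost is a sentence or two of text and two degrees of freedom (118 to 116). Both factors are already recorded in order to randomize. The sample size does not change.
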